The sample size for the main trial results was calculated to assess the treatment effect separately in each MC type group (1/2). In each MC type group, the study was designed to detect ($\beta = 0.1$, two-sided $\alpha = 0.05$) a mean difference of 4 (SD 5) in the RMDQ score between the two treatment groups (amoxicillin or placebo) at one-year follow-up. In total 180 patients were actually included (intention to treat population), 118 in the MC type 1 group and 62 in the MC type 2 group (16).

The trial protocol gives further details regarding sample size calculation and trial methods (1).

The AIM trial showed a statistically significant – but not clinically important – effect of Amoxicillin in the type 1 MC group, but no effect in the in the type 2 MC group (16). Subgroup analyses indicated a clinically relevant effect in patients with MC related oedema on MRI STIR sequences/series (7) and possibly also a borderline clinically relevant effect in younger patients (aged < 40 years)(6).

Patients

Patients included in this present study were a selected group with as ‘pure’ MC types as possible, who gave consent to participate in the AIM trial, and who provided blood samples and underwent MRI prior to enrolment. Of those selected 78 subjects were eventually randomized and took part in the AIM trial, 6 subjects did not satisfy the AIM eligibility criteria and were not included in the AIM trial (figure 1).

The selection criteria for this present study were, firstly, that two study radiologists agreed that the MRI inclusion criteria of the AIM trial (52) were fulfilled (i.e., type 1 and/or type 2 MCs with height \geq 10% of vertebral body height and diameter > 5 millimeters existed at the level of a prior disc herniation (index level)). Secondly, that type 1 was the most extensive MC type at two or more index level endplates (categorized as MC1, n=47) or that type 2, but not type 1, existed at the index level (categorized as MC2, n=48). From this selected group we included 84 subjects (46 MC1, and 37 MC2) in the present study.

Controls

Statistical Analysis Plan for analysis of cytokines as prognostic factors and predictors of antibiotic treatment effect in patients with chronic low back pain and Modic changes (the AIM trial) - - version 1.0

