To explore potential predictors of treatment effect we will perform six main analyses (1A, 1B, 1C, 2A, 3A, 3B) of predictors of antibiotic treatment effect (Table 2). All six analyses will be performed using multiple regression with RMDQ score at one year as dependent variable and the interaction term (predictor*treatment group) as independent variable adjusted for baseline RMDQ score, the potential predictor, the treatment group, the randomization stratification variables (MC type (1/2) and for former disc herniation surgery (yes/no)).

We will only use the baseline value for any potential predictor of treatment effect and for any covariate. Within each category (subgroup) of categorical variables, we will report the treatment effect predicted in the interaction term analysis by marginalizing (using the margins command in Stata) over the other covariates (and not perform a separate stratified analysis).

We will present results of analyses 1A, 1B, 1C, 2A, 3A and 3B in a forest plot of effect estimates for each potential predictor of treatment effect with 95 % CIs and the p value for the interaction (predictor *treatment group). The overall treatment effect will be marked on the plot (56). The plot will also show the treatment effect within subgroups.

Table 2 –Main analyses of cytokine-defined predictors of treatment effect

| Hypothesis and rationale | Variables and subgroups | Analysis |
|--|---|---|

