-Independence of effect: If the treatment effect (difference in RMDQ score at 1 year follow-up between antibiotic and placebo groups) are more than 4 RMDQ points in any of the main analyses 1(A, B, or C), 2(A), or 3(A or B) we will repeat the same analysis including interaction terms of all such relevant variables x treatment group, age (dichotomized as above or below 40 years) x treatment group and STIR composite variable x treatment group (without the individual covariates age and STIR composite variable) in the same regression analysis (59). Both age and STIR composite variable modified the treatment effect in our prior analyses.

Analyses of cytokines as prognostic factors (hypothesis 2)

For hypothesis 2, we define eleven main analyses (1, 2A, 2B, 3, 4A, 4B, 5A-E) of prognostic factors. These main analyses are ranked in order, from what we consider most to least likely to be prognostic factors (based on prior evidence and knowledge of cytokines).

Main analyses

We will perform linear regression models as main analyses that all will have the following in common:

-Relative change in RMDQ from baseline to one-year follow-up will be dependent variable. This differs from other analyses in the AIM trial (RMDQ at one-year follow-up was dependent variable) because we here consider it problematic to adjust for baseline RMDQ-score as it could induce bias (due to regression to the mean or horse-riding / collider problems) (60). Such adjustment could on the other hand also be highly desirable because baseline score is thought to be one of the most important predictors of future follow-up scores (61, 62). Our choice of dependent variable attempts to take the baseline value into account, while avoiding the possible problem related to adjusting for the baseline value.

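### The independence check for hypothesis 1 omits MC type x treatment, so it cannot show whether a cytokine predictor is separate from MC type

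*SAP*

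**What the plan says.** The SAP, section The AIM-trial, states that AIM was sized to assess treatment separately in each MC type group, with "118 in the MC type 1 group and 62 in the MC type 2 group". It summarises the result as a statistically significant "effect of Amoxicillin in the type 1 MC group, but no effect in the in the type 2 MC group", with the explicit qualification that the type 1 effect was not clinically important. No MC type x treatment test is given.

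The section Patients describes the cytokine sample as "a selected group with as ‘pure’ MC types as possible". MC1 required that "type 1 was the most extensive MC type at two or more index level endplates"; MC2 required type 2 and no type 1 at the index level.

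Under Inferential statistics, all six hypothesis 1 regressions (1A, 1B, 1C, 2A, 3A, 3B) adjust for baseline RMDQ, the predictor, treatment and "the randomization stratification variables (MC type (1/2) and for former disc herniation surgery (yes/no". MC type is therefore a main effect in each. The supportive mixed model also has it as a main effect only.

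The paragraph Independence of effect applies when a treatment effect in a main analysis exceeds 4 RMDQ points. It adds interactions with treatment for the relevant predictors, for age and for the STIR composite, and gives the reason: "Both age and STIR composite variable modified the treatment effect in our prior analyses". MC type x treatment is not listed. Table 4 names independence of a significant subgroup effect as one of the credibility criteria.

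**The concern.** A main effect of MC type shifts the expected RMDQ score equally in both arms. It does not let the amoxicillin effect differ by type. If the effect does differ by type, and a cytokine group holds more type 1 patients than its comparator, the cytokine x treatment term picks up part of the difference between types.

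The independence check is where the plan would detect this, and it leaves out the variable on which the sample was selected. A cytokine finding could then partly restate a contrast already visible on MRI, and Table 4's independence criterion could not be answered for MC type. In analyses 1A to 1C, stage 1 searches for splits by their interaction with treatment and MC type is not a candidate variable, so a cytokine split that partly stands in for MC type could be selected.

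**Working it through.** **The plan's own figures first.** For analysis 2A the SAP uses cells of 13 and 24 (categories 1+2, placebo and amoxicillin) and 19 and 22 (categories 3+4), SD 5 and two-sided alpha 0.05.

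- Standard error of the interaction contrast: 5 x sqrt(1/13 + 1/24 + 1/19 + 1/22) = 5 x sqrt(0.2167) = 2.327.
- Power for a 6-point interaction, noncentral F with 1 and 74 degrees of freedom: 0.7205 (SAP: 0.72).
- Interaction detectable with 80% power: 6.61 points (SAP: 6.6).

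Both figures reproduce.

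**Size of the leak.** Let D be the difference in treatment effect between type 1 and type 2, and Δ the difference in type 1 share between categories 1+2 and 3+4. If MC type is the only true modifier, the effect in a cytokine group is (effect in type 2) + D x (type 1 share in that group). The difference between the two cytokine groups is then D x Δ, although cytokines modify nothing.

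**Inputs the SAP does not give, taken as assumptions.**

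- D from 2 to 4 points. If the type 1 effect was below the 4-point relevance threshold and the type 2 effect was about zero, 4 is a ceiling.
- Δ from 0 to 0.8.
- Overall type 1 share 46/83 = 0.55, from "From this selected group we included 84 subjects (46 MC1, and 37 MC2) in the present study". The two counts sum to 83, and the split among the 78 randomised patients is not stated.

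With 37 patients in categories 1+2 and 41 in 3+4, Δ = 0.6 means a share of 0.554 - 0.6 x 37/78 = 0.27 in categories 3+4 and 0.87 in 1+2.

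The 2A regression (treatment, category, MC type, category x treatment) was evaluated at its exact expectation with these cells, with and without MC type x treatment. Baseline RMDQ and former surgery were left out. The chance of p < 0.05 refers to the cytokine interaction when cytokines modify nothing. The power column gives power for a true 6-point cytokine interaction once MC type x treatment is added.

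| Δ | Leak, D = 2 | Chance of p < 0.05, D = 2 | Leak, D = 4 | Chance of p < 0.05, D = 4 | Power with the term added |
|---|---|---|---|---|---|
| 0.2 | 0.43 | 0.054 | 0.86 | 0.066 | 0.70 |
| 0.4 | 0.79 | 0.063 | 1.58 | 0.103 | 0.65 |
| 0.6 | 1.18 | 0.079 | 2.37 | 0.171 | 0.54 |
| 0.8 | 1.64 | 0.106 | 3.27 | 0.283 | 0.32 |

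Leaks are in RMDQ points. They differ slightly from D x Δ (for example 4 x 0.8 = 3.2 against 3.27) because patients were allotted to types in whole numbers. At Δ = 0 the leak is essentially nil and the rejection rate is 0.05. With MC type x treatment in the model, the leak is 0 and the rejection rate 0.05 in every row. The price is a larger standard error for the cytokine interaction: from 2.33 to 2.38, 2.53, 2.88 and 4.00 down the rows.

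**The case against.** The SAP chose age and STIR by a stated rule: both had modified the effect in earlier analyses. It reports no such result for MC type. A reader might infer from the AIM summary that MC type is an established effect modifier. The document does not support that. Significance in 118 patients and no effect in 62 is not an interaction test, and the type 1 effect is described as not clinically important. This stands, and it is why D is an assumption with 4 as a ceiling.

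Nothing in the SAP links any cytokine category, principal component or mined subgroup to MC type. Choosing clear-cut types sharpens the imaging contrast but does not create that link. This also stands: the leak may be nil.

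STIR reflects MC-related oedema and type 1 is the oedema type, so STIR x treatment covers part of the same pathway. That is so, but only in part, because STIR and MC type are different variables.

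The SAP labels everything exploratory, treats differences under 4 points as not clinically relevant, and says for analysis 2 that interpretation will rest on effect size more than p values. Objective 1 asks whether profiles predict the effect, not whether they add to known factors. These points lower the weight. They do not remove the gap, because the plan itself sets out to assess independence, and the forest plot will show interaction p values whether or not the 4-point trigger is met.

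**Conclusion.** The gap is real but modest. The plan adjusts for MC type only as a main effect and omits MC type x treatment from the one analysis meant to test independence. Under the assumed ranges, the leak into the 2A cytokine interaction is 0.4 to 1.6 points for a 2-point type difference and at most about 3.3 points for a 4-point difference. It needs an association between cytokines and MC type that the SAP neither reports nor rules out. Alone it stays below 4 points, so the likelier harm is an inflated estimate or nominal p value, not a clinically relevant finding created from nothing.

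Two stronger readings should be resisted. One is that a mined subgroup would separate the types completely and carry the whole type difference; nothing in the SAP suggests so close an alignment. The other is that the term belongs in all six main models, or that a cytokine predictor must pass it to be reported. The power loss is large exactly where the association is strong, so a hard rule would often be uninformative with 78 patients.

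**What to change.** Leave the six main models as they are. In the independence-of-effect sensitivity model, add MC type x treatment beside the age and STIR interactions; the MC type main effect is already in the model. Tabulate MC type by cytokine subgroup and treatment group for each categorical predictor, so that the strength of any association can be seen even where the 4-point trigger is not met. State that a cytokine predictor will be described as independent of MC type only in the light of that sensitivity estimate and its interval.

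The cost is one model term, one table and a few lines of text, with no new data. The interval for the cytokine interaction will widen: slightly if the association is weak (power 0.72 to 0.70 at a share difference of 0.2) and substantially if it is strong (0.72 to 0.32 at 0.8). For that reason the result should inform interpretation and not act as a pass/fail rule for the main analyses.

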1. To evaluate whether certain profiles of serum cytokine levels predict any treatment effect of 3 months oral amoxicillin in patients with chronic low back pain and type 1 or 2 MCs at the level of a previous lumbar disc herniation (cytokines as predictors of antibiotic treatment effect)
2. To evaluate whether certain profiles of systemic serum cytokine levels provide added prognostic value over known prognostic factors in patients with chronic low back pain and type 1 or 2 MCs at the level of a previous lumbar disc herniation (cytokines as prognostic factors independent of treatment)

Hypotheses

For each objective (1 and 2 above), we made respective hypotheses that

1. Patients with a certain pattern of serum cytokine levels at baseline in the antibiotic group report a significantly lower RMDQ score at one-year follow-up than patients with the similar cytokine pattern in the placebo group
2. Serum proinflammatory cytokine levels are associated with change in RMDQ score from baseline to one-year follow-up, given known prognostic factors.

Statistical principles

All analyses described in this plan are considered *exploratory* in the sense that the present objectives were not described in the original protocol, and are performed after results for treatment efficacy in the main trial (5) and in clinical and radiological subgroups (6, 7) were available. Any additional analyses not described in this SAP will be identified as *post hoc* in the article. Some analyses are based on *pre-defined subgroups*, (e.g. defined in advance of analyses), others on *post-defined subgroups*, meaning that subgroups will be defined by a data-driven approach.

All outcomes are analysed for superiority of one intervention compared to the other (hypothesis 1) or of having compared to not having a prognostic factor (hypothesis 2). All relevant statistical tests will be 2-sided and the nominal p value will be reported. All confidence intervals presented will be 95% and 2-sided. The assumption of normal distribution will be checked by visual inspection of a QQ-plot.

Statistical Analysis Plan for analysis of cytokines as prognostic factors and predictors of antibiotic treatment effect in patients with chronic low back pain and Modic changes (the AIM trial) - - version 1.0

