-Due to power limitations we will restrict the number of covariates/independent variables to eight (10 patients/independent variable)(63). Based on suspected prognostic factors for LBP disability (61, 62) and suspected factors associated with serum cytokine levels (64, 65), we will add the following as covariates into the model due to possible confounding: age, leg pain (0-10 NRS), fear avoidance, emotional distress (dichotomized into HSCL-25 $\geq 1,75$ and $< 1,75$), psychiatric comorbidity (yes/no), other specific comorbidity (numerical, one point for each of rheumatoid arthritis, osteoarthritis, Diabetic, Cardiac/pulmonary) and sick leave (categorized into 1. working full time, 2. partial sick leave and 3. complete sick leave / disability pension / unemployed / student/other/unknown). Age, leg pain and fear avoidance will be continuous variables.

For each model we will evaluate:

1. The predictiveness by comparing the multiple correlation coefficient R^2 of the complete model with the R^2 in the model without the independent variable of interest (66).
2. The effect size described in terms of relative change in RMDQ. We will consider effect size $>30\%$ as clinically relevant, which equates approximately to a difference of 4 out of 12.8 (at baseline) RMDQ points.

The following models (1, 2A, 2B, 3, 4A, 4B, 5A, 5B, 5C, 5D, 5E) will differ in choice of independent variable of interest, which will be:

1. Cytokine category group based on cytokine classification group (4 categories of patients, figure 2). Each category of patients will be assessed versus the three other categories combined.
2. Classification variable defined by a Recursive Partitioning analysis using RPART command in R. Relative change in RMDQ from baseline to one-year follow-up will be dependent variable. Only patients nonmissing values in both baseline and one-year follow-up RMDQ score will be included. Stopping conditions will be $\text{maxdepth}=3$ and n_{min} (minimal number of observations in terminal/leaf node)=5. We will use tenfold cross-validation and a complexity parameter of 0,01. We will perform two Recursive Partitioning models that differs only in what variables that are included:

Statistical Analysis Plan for analysis of cytokines as prognostic factors and predictors of antibiotic treatment effect in patients with chronic low back pain and Modic changes (the AIM trial) - - version 1.0

- A. all 39 cytokines

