- B. all 39 cytokines, age, leg pain (0-10 NRS), fear avoidance, emotional distress, psychiatric comorbidity (yes or no), physical workload, and sick leave.
In models 2A and 2B we will use cytokine variables as categorical with cutoffs at -2, -1.5, -1, -0.5, 0, 0.5, 1, 1.5 and 2 SD above the mean in the healthy control groups, and other variables as defined for the linear regression analyses above. Physical workload will be categorized into 1. mostly sitting, 2. job requires a lot of walking and 3. job requires a lot of walking and lifting / job requires physically heavy work.
3. Abnormal cytokine values, based on PCA analysis of healthy controls and patients with MCs (figure 3), dichotomized into normal (inside yellow circle) and abnormal (outside yellow circle) cytokine levels.
4. Principal component 1 (continuous variable) from
 - A. PCA analysis 3A of cytokines as predictors of treatment effect
 - B. PCA analysis 3B of cytokines as predictors of treatment effect
5. Individual cytokines categorized with cutoffs at 0, 1 and 2 SD above the mean in the healthy control groups
 - A. MIF levels
 - B. TNF α levels (67)
 - C. IL-6 levels
 - D. IL-8 levels
 - E. IL-1 β levels

For model 2B we will avoid adding any covariate that is also used to define the independent variable of interest. E.g. if the recursive partitioning model define the independent variable based on age and leg pain, we will exclude age and leg pain as covariates in the final linear regression model.

For all models a sample size (n=78) will, assuming an R^2 of 30% in the incomplete model including seven known prognostic factors but without the one independent variable of interest (estimates of R^2 in models excluding baseline values are 20-30% (68, 69)), give a power ($\alpha=0.05$, $\beta=0.2$) to detect increases of 7% (absolute percentage points) in R^2 in the complete model with one variable of interest and seven covariates (using the 'power rsquared' function in Stata). For model 1, detecting a difference of 30% in change from baseline RMDQ (SD 5) between two groups of n=28 and n=44 will give a power ($\alpha=0.05$) of 90% (using the 'power oneway' function in Stata).

Table 3 – Main analyses of cytokine-defined prognostic factors

| Hypothesis and rationale | Variables and subgroups | Analysis |
|---|--|------------|

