With 30% improvement of RMDQ from baseline to one-year follow-up as the gold standard status (diagnostic variable), we will calculate Area under ROC curve (AUC), cutoff value, positive predictive value, negative predictive value, sensitivity and specificity for each independent variable of main analyses (1, 2A and 2B) as a prognostic variable of interest (test variable). We will consider the same calculations for each independent variable of the additional analyses (3 to 5).

Assess the direct effect of cytokines on relative change in RMDQ score (baseline to 1-year) in the possible case that baseline value of RMDQ mediates any overall/total effect:

For each linear regression model of the main analyses (1, 2A and 2B) we will perform the same analysis including baseline value of RMDQ as a covariate. These models could also be interpreted to provide estimates of the prognostic effect (without causal inference) of cytokines given a specific baseline value, and we can therefore safely ignore the possible problems with bias mentioned above (under Main analyses). We will consider the same sensitivity analysis for each linear regression model of the main analyses (3 to 5).

Assess the effect of cytokines on relative change in RMDQ score (baseline to 1-year) in the placebo group only, in the possible case that that the subgroup predicts treatment effect:

We will consider (depending on results and power), for each linear regression model of the analyses 1, 4 and 5, performing the same analysis including only patients in the placebo group.

Internal validation

We will consider internal validation on any analyses 1 to 5 (depending on results) by using bootstrapping.

Sensitivity analyses:

The following sensitivity analyses will be performed for the main analyses (1, 2A and 2B), and will be considered performed for the main analyses 3 to 5:

Assess the possibility that covariates included in main analyses are non-confounders/mediators:

For each linear regression model of the main analyses 1, 2A and 2B, we will perform unadjusted analysis with relative change in RMDQ from baseline to one-year follow-up as dependent variable, and the same independent variable as used in each respective model (1, 2A and 2B). These unadjusted analyses are recommended as we cannot rule out the possibility that the covariates included in the main analyses could be non-confounders or mediators (72). Each model will be compared to their respective main analysis by assessing R^2 .

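### Added prognostic value is measured by the raw in-sample R² gain, which is biased upward (slightly for the pre-defined variables, seriously for the tree models 2A and 2B), and optimism correction is optional

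*SAP*

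**What the plan says.** The second aim in the SAP's Objectives section is to learn whether cytokine profiles "provide added prognostic value over known prognostic factors in patients with chronic low back pain". Under Analyses of cytokines as prognostic factors (hypothesis 2), "we define eleven main analyses (1, 2A, 2B, 3, 4A, 4B, 5A-E) of prognostic factors". Main analyses then lists two things to evaluate for every model. The first is predictiveness, obtained by "comparing the multiple correlation coefficient R^2 of the complete model with the R^2 in the model without the independent variable of interest". The second is effect size, with a relative RMDQ change above 30% called clinically relevant.

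The R² in item 1 is the ordinary one. No adjusted, cross-validated or optimism-corrected version appears anywhere in the SAP, and the unadjusted and other-confounder sensitivity models are also compared on R². Under Internal validation the SAP says: "We will consider internal validation on any analyses 1 to 5 (depending on results) by using bootstrapping". The ROC and predictive-value calculations carry an internal-validation label, but no resampling or hold-out is described for them.

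For 2A and 2B the cytokine variable is the output of a recursive partitioning tree (depth 3, at least five patients per leaf, complexity parameter 0.01). The tree's outcome is relative RMDQ change, which is also the outcome of the regression that follows. Tenfold cross-validation is mentioned for the tree, without a rule for using it to choose tree size.

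**The concern.** Adding any variable to a least-squares model leaves in-sample R² unchanged or raises it. The gain planned as the measure of added predictiveness is therefore biased upward, and the bias grows with the number of parameters added. It grows much further when the variable was itself built by searching for the best fit to the same outcome. Followed as written, the plan can report a gain for an uninformative cytokine variable with nothing beside it to show what chance alone would give.

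The correction that would deal with this, bootstrapping, is conditional on seeing the results. The published gains could then be corrected for some models and not for others. The stake is how far objective 2 can be believed, above all for 2A and 2B, which rank directly after model 1.

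**Working it through.** **Inputs.** n=78, seven covariates, reduced-model R² 0.30, one variable of interest, α=0.05, power 0.80 (SAP, power paragraph for hypothesis 2). That paragraph reads "For all models a sample size (n=78) will, assuming an R^2 of 30% in the incomplete model including seven known prognostic factors", and adds that "estimates of R^2 in models excluding baseline values are 20-30" per cent. Tree sample: 45 + 27 = 72 patients with RMDQ at both times (Table 5B).

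**Parameters added, k.** One for each model 1 contrast and for 3, 4A and 4B. Three for 5A to 5E, since cut-offs at 0, 1 and 2 SD make four bands. For 2A and 2B, up to eight leaves, so up to seven parameters.

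**1. The SAP's own figure.** The SAP claims power "to detect increases of 7% (absolute percentage points) in R^2 in the complete model".
- f² = 0.07/(1 − 0.37) = 0.111; noncentrality = 78 × 0.111 = 8.67; df = (1, 69). Power is 0.827.
- The gain detectable at 80% power is 6.6 points, which rounds to 7. The figure reproduces for one tested parameter.
- With three tested parameters, power at 7 points is 0.665 and the detectable gain is 9.0 points.

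**2. Expected gain under no effect, pre-defined variables.** Formula: (1 − R² reduced) × k/(n − 1 − number of covariate parameters).
- k=1: 0.70 × 1/70 = 1.0 point; 95th percentile 3.8.
- k=3: 0.70 × 3/70 = 3.0 points; 95th percentile 7.7.
- Counting sick leave as two parameters (eight in all) changes little: 0.70/69 = 1.0 and 2.1/69 = 3.0 points; 95th percentiles 3.9 and 7.8.
- At R² 0.20: 0.80/70 = 1.1 and 2.4/70 = 3.4 points.

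These take 30% as the R² observed in the sample. If 30% is the population value, the covariates also overfit. The expected unexplained share falls to 0.70 × 70/77 = 0.636, and the null gains become 0.636/70 = 0.9 and 3 × 0.636/70 = 2.7 points. Simulation gave 0.9 and about 2.6, and never a negative gain.

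**3. Adjusted R² repairs these models.** Adjusted R² = 1 − (1 − R²)(n − 1)/(n − p − 1).
- Reduced, p=7, R² 0.30: 1 − 0.70 × 77/70 = 0.23.
- One noise parameter, p=8, R² 0.31: 1 − 0.69 × 77/69 = 0.23.
- Three noise parameters, p=10, R² 0.33: 1 − 0.67 × 77/67 = 0.23.

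The average null gain becomes zero.

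**4. Tree models.** Null simulation of a 2A-type analysis: n=72; seven covariates with population R² 0.30; 39 noise cytokines in ten ordered categories at the SAP's cut-offs; depth 3, leaf size at least 5, complexity 0.01. Assumed: correlation 0.3 between cytokines (0 gave similar results) and at least 15 patients in a node before splitting (20 gave similar results).

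| Tree | Null trees that split | Mean raw gain if split | Naive F test p<0.05 if split |
|---|---|---|---|
| Unpruned | 100% | 19.8 points | 99% |
| Pruned at minimum cross-validated error | 10.5% | 12.7 points | 98% |
| Pruned by the 1-SE rule | 3.75% | 13.9 points | 100% |

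Further runs of the unpruned tree gave mean gains from about 17 to 21 points. Adjusted R² still rose by about 16 to 20. Arithmetic shows why: with R² going from 0.30 to 0.50 on four leaf parameters, adjusted R² goes from 1 − 0.70 × 71/64 = 0.22 to 1 − 0.50 × 71/60 = 0.41. The adjustment charges for four parameters, not for the search over 39 cytokines and their cut-points. Even a single data-driven split gained 5.0 points on average, against about 1 for a pre-specified dichotomy.

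**5. Model 2B.** Covariates used by the tree are dropped from the regression, and the reference model is not stated. If the reference keeps only the remaining covariates, the gain also credits the tree with what the known factors contribute. If it keeps all seven, the two models are not nested and the difference can be negative.

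**The case against.** R² gain is not the only criterion. Effect size is evaluated beside it, nominal p values and a two-sided α of 0.05 are stated, and the power calculation rests on an F test of the R² increment, which accounts for parameters in the pre-defined models. All analyses are declared exploratory. A null gain of about 1 point in the one-parameter models is small, and 5A to 5E rank last, with their coding not spelled out. Bootstrapping is at least named, and it matters most for results that look positive.

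Most of this stands, and it limits the point for the pre-defined models. It does not make raw R² an unbiased measure of predictiveness, and the F test is not tied to the R² comparison. It does not help 2A and 2B, where the F test is itself invalid. Cross-validated pruning, if used, makes null splits rarer but leaves the R² of the trees that do split uncorrected.

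A reader might infer two stronger things that the SAP does not support:
- **That a noise gain above 7 points is a false-positive finding.** The 7 points are a detectable gain in a power statement, not a decision rule.
- **That four-band cytokines would be ranked above principal component 1 for having more parameters.** Each complete model is compared with its own reduced model, the order of the models is fixed beforehand on prior evidence, and no ranking by R² gain is planned.

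Nor does the SAP say that any positive gain counts as added value.

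**Conclusion.** The point holds. The planned measure of added predictiveness is biased upward, and its correction is optional and dependent on results. The size is uneven: about 1 point for the model 1 contrasts, 3, 4A and 4B; about 2.6 to 3 points for 5A to 5E if coded as four bands; and about 17 to 20 points for an unpruned tree in 2A. Among null trees that survive cross-validated pruning, the gain is about 13 to 14 points. For 2B the reference model is also undefined, so the guarantee of a non-negative gain may not apply there.

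The figures for pre-defined variables rest on n=78 and the SAP's assumed 30%; at 20% they are slightly larger. The tree figures rest on simulation with an assumed cytokine correlation and ordered categories. Their exact values will differ in the real data. This should be changed before analysis; the exploratory label softens the consequence without removing the bias.

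**What to change.** - **Models 1, 3, 4A, 4B and 5A to 5E:** replace the raw R² comparison with the change in adjusted R² (or bootstrap optimism-corrected R²), with a 95% confidence interval and the partial F test. State the coding of 5A to 5E.
- **Models 2A and 2B:** report an optimism-corrected R² gain from a bootstrap or cross-validation in which tree growing, any pruning and the regression are all repeated in every resample. Do not rely on adjusted R² or the F test here. State how tenfold cross-validation sets tree size.
- **Model 2B:** name the reference model for the R² comparison.
- **Internal validation:** make it unconditional by deleting both the word 'consider' and the dependence on results, so that every model is reported in the same way whatever it shows.

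The cost is SAP wording and some computing, including a decision on how resampling is combined with the fifty imputations. No new data are needed. The reported gains will be smaller, markedly so for 2A and 2B if their trees are noise.
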